#### Sirolimus drug interactions, co-administration of calcineurin inhibitors, and dosemodification for concurrent azole therapy

#### **Drug interactions:**

Sirolimus is a substrate for cytochrome CYP 3A4 and a P-glycoprotein (P-gp). Drugs that may increase sirolimus blood concentrations include CYP 3A4, 5, or P-gp inhibitors:

- Calcineurin inhibitors: Simultaneous administration of cyclosporine soft gelatin capsules (Neoral®) results substantial increases in the sirolimus Cmax and AUC. This is avoided if sirolimus is taken 4 hours after administration of cyclosporine.
- Calcium Channel Blockers: diltiazem, nicardipine, nifedipine, verapamil and amlodipine. Sirolimus should be monitored and a dose adjustment may be necessary.
- Triazole antifungal agents: fluconazole, itraconazole, clotrimazole, posaconazole, isavuconazole voriconazole and ketoconazole. The magnitude of increases sirolimus Cmax, tmax, and AUC is such that sirolimus should be administered cautiously together with fluconazole, itraconazole, or posaconazole, and with extreme caution if administered together with voriconazole or isavuconazole. If co-administration is unavoidable, then the dose of sirolimus should be greatly reduced at the time of initiation of the antifungal medication as recommended in Table 2 and that there should be very frequent monitoring of trough concentrations of sirolimus in whole blood. Sirolimus concentrations should be measured upon initiation, during co-administration, and at discontinuation of antifungal treatment, with sirolimus doses adjusted accordingly.
- Macrolide antibiotics: clarithromycin, erthyromycin, telithromycin, troleandomycin (but NOT azithromycin).
- Gastrointestinal prokinetics: cisapride, metocloproramide.

Drugs that may decrease sirolimus blood concentrations include CYP 3A4, 5, 7 or P-gp inducers:

- Anticonvulsants: carbamazepine, Phenobarbital, phenytoin.
- Antibiotics: Rifampin, rifanpentine.
- Herbs: St. John's Wort (*Hypericum perforatum*).

Care should be taken when other drugs or substances that are metabolized by CYP3A4 or Pglycoprotein are administered concomitantly with sirolimus. Grapefruit juice reduced CYP3A4 mediated metabolism of sirolimus and must not be used for dilution.

#### **Co-administration of calcineurin inhibitors:**

#### When co-administered with sirolimus, recommend target levels are as follows:

The target serum level for **tacrolimus** is **3-7 ng/mL** 

The target serum level for cyclosporine is 120-200 ng/mL

Dose adjustments are based upon clinical judgment of the managing physician after considering clinical toxicity, serum levels, GVHD, concomitant drug use and the rate of rise or decline of the serum level. Following represent *suggested* dose adjustments in calcineurin inhibitors, when initiating sirolimus to achieve target levels specified above.

Calcineurin inhibitor actual serum level prior to initiating sirolimus	Recommended target serum level for calcineurin inhibitors when co- administered with sirolimus	Recommended dose adjustment to achieve recommended target serum level
tacrolimus > 10 ng/mL	tacrolimus = 3-7 ng/mL	50% dose reduction
tacrolimus = 7.1-10 ng/mL	tacrolimus = 3-7 ng/mL	33% dose reduction
tacrolimus $\leq$ 7.0 ng/mL	tacrolimus = 3-7 ng/mL	No change
cyclosporine > 400 ng/mL	cyclosporine = 120-200 ng/mL	50% dose reduction
cyclosporine = 201-399 ng/mL	cyclosporine = 120-200 ng/mL	33% dose reduction
cyclosporine $\leq 200 \text{ ng/mL}$	cyclosporine = 120-200 ng/mL	No change

\*When calcineurin inhibitors (cyclosporine, tacrolimus) are given with prednisone (i.e. among patients not randomized to the sirolimus arm of this trial), standard practices are recommended for dosing/monitoring of these agents. Suggested target levels for these agents in the absence of sirolimus are cyclosporine 200-400ng/mL and tacrolimus 5-15ng/mL. Again, these are recommendations (not protocol mandated), and management is directed by the treating physician.

#### **Dose-modification in setting of azole therapy:**

Antifungal prophylaxis: Triazole antifungal medications are expected to increase serum CNI and sirolimus levels, therefore, dosages of CNIs and sirolimus, should be adjusted accordingly using the guidelines recommended in Table 2 and 3.

# TABLE 2 - PRE-EMPTIVE DOSE REDUCTION OF SIROLIMUS OR CNIS WHEN AZOLES ARE INITIATED AT STEADY STATE LEVELS OF SIROLIMUS OR CNIS

Antifungal	Cyclosporine	Tacrolimus	Sirolimus
	Dose $\downarrow$	Dose $\downarrow$	Dose $\downarrow$
Voriconazole	50%	67%	90%
Posaconazole	25%	67%	90%
Isavuconazole	50%	67%	90%
Itraconazole	50%	50%	ND
Fluconazole	25%	25%	50%

\*Notes:

I. If voriconazole must be added to control fungal infection then following the 90% reduction in sirolimus dosing and/or 50%-67% reduction in CNI dosing SRL and/or CNI serum levels should be measured 24-48 hours later and then every 3-4 days until levels are stable and in the desired range. If voriconazole is given intravenously or if voriconazole and sirolimus are not given together, these guidelines may not apply because the effect on bioavailability of sirolimus will be weaker.

- 2. Note that sirolimus tablets should not be split or crushed. Fractional dose of sirolimus may be achieved by drawing an appropriate volume of the 1 mg/mL oral liquid formulation into a 1 mL syringe and swallowed directly (or mixed with water or orange juice; no other liquids, including grapefruit juice, should be used for dilution).
- 3. If posaconazole or itraconazole or high-dose fluconazole are added then SRL and/or CNI serum levels should be followed 48-72 hours later and then every 3-5 days until levels are stable and in the desired range.

# TABLE 3 - ANTICIPATE DOSE INCREASE OF SIROLIMUS OR CNIs WHENAZOLES ARE STOPPED DURING CONCOMITANT SIROLIMUS OR CNI THERAPY

Antifungal	Cyclosporine		Tacrolimus		Sirolimus	
	Dose ↑	Comment	Dose ↑	Comment	Dose ↑	Comment
Voriconazole	2-fold	Dose increase	3-fold	Dose increase	10-fold	Dose increase
Posaconazole	1.3-	may not be	3-fold	may not be	ND	may not be
	fold	necessary for		necessary for		necessary for
Isavuconazole	2-fold	5-10 days	3-fold	5-10 days	10-fold	5-10 days
Itraconazole	2-fold		2-fold		ND	
Fluconazole	1.3-		1.3-fold		2-fold	
	fold					

**Note:** Although sirolimus and CNI doses may need to be substantially increased when azole therapy is stopped, the azole mediated inhibition of cytochrome CYP 3A4 (and other) and P-glycoprotein may take 5-10 days to abate and therefore immediate dose increases are not advised. Rather, sirolimus and CNI dose increases should be cautious and based on more frequent monitoring of the sirolimus and/or CNI levels as appropriate.

#### Additional considerations for calcineurin inhibitor (CNI) therapy:

- *Children* generally require a larger total daily dose of CNI by weight than adults. If aged < 6 years, every 8 hour administration may be required to maintain desirable serum trough levels. For those patients in whom adequate serum trough levels cannot be maintained using intermittent oral or IV dosing, continuous IV infusion may be warranted.
- *Review of concomitant medications for potential interactions that may significantly alter serum CNIs levels is essential* because CNIs undergo extensive metabolism by the hepatic and intestinal cytochrome P-450 system which may impact toxicity and efficacy of CNIs.
- Although elevated CNI blood levels are more frequently associated with toxicity (especially renal or hepatic), *"therapeutic" CNI blood levels may also be associated with toxicity* (e.g. significant tremors). Therefore, dose decreases are recommended for significant organ toxicities that manifest despite a "therapeutic" CNI level.
- *Emesis*: A repeat dose of CNI may be given if emesis happens within 15 minutes of taking the planned dose.
- CNIs should be administered at a consistent time each day and in relation to meals. Neoral oral solution should be administered in orange or apple juice at room temperature.

- Subjects should *avoid beverages containing the enzyme bergamottin* (grapefruit juice, Sunny Delight, Fresca, and Squirt) when taking CNIs.
- *Distal paraesthetic pain or burning during the infusion* may be alleviated by extending the IV infusion time for Sandimmune from the standard of 1 hour to as long as 6 hours. Alternatively, cyclosporine may be administered as a continuous infusion over 24 hours for patients intolerant of intermittent administration.
- Monitor closely for an acute allergic reaction for the first 30 minutes after starting tacrolimus IV infusion and at frequent intervals thereafter.
- Intravenous route of administration is preferred for patients with progressive GVHD of the liver or gastro-intestinal tract until GVHD is clinically improved and the oral route reliable.

Starting Oral Formulation	Conversion to IV formulation	
Prograf®	IV $Prograf = 0.25 x$ total daily dose of oral Prograf but should be	
	given as continuous daily infusion	
Neoral®	IV Sandimmune = $0.4 \text{ x}$ total daily dose of Neoral	
Gengraf®	IV Sandimmune = $0.4 \text{ x}$ total daily dose of Gengraf	
Sandimmune®	IV Sandimmune = $0.25 \text{ x}$ total daily dose of oral Sandimmune	

• If the oral route becomes temporarily unfeasible and conversion to the intravenous formulation is required the following recommendations are made:

#### 2.5.4. Prednisone

Patients randomized to steroids will receive prednisone 2mg/kg/day PO (or methylprednisolone 1.6 mg/kg/day IV). Patients unable to take tablets can use oral prednisolone solution 2 mg/kg/day. For patients that weigh over 100kg, maximal starting dose of prednisone will be 200mg (or 2mg/kg based on a modified starting weight of 100kg). For calculation of subsequent prednisone doses/kg on subsequent measures, the modified starting weight of 100kg will be used.

#### **Duration of Steroids and Taper**

All patients should receive prednisone 2mg/kg/day PO (or methylprednisolone 1.6 mg/kg/day IV) for at least 3 full days (72 hours). This starting dose was carefully selected for the following reasons: (1) Both the clinical and biomarker-based risk stratification systems have been developed in the setting of patients treated with this starting prednisone dose; (2) The 2mg/kg/day starting dose was used in both BMT CTN 0302 and CTN 0802 trials, and expected prednisone response rates and allied power calculations for this trial are derived from this preliminary data; (3) Variable starting doses would confound the analysis of prednisone taper in this trial; (4) Prior randomized clinical trial data supported greater requirement for secondary systemic immune suppressive therapy in those treated with 1mg/kg vs. 2mg/kg starting dose. Thereafter (after 72 hours of 2mg/kg/day dose), the decision of when and how to taper is at the discretion of the treating physician. A potential prednisone taper is provided in Appendix E.

# 2.5.5. GVHD Prophylaxis Medications

Medications such as cyclosporine and tacrolimus (if used as GVHD prophylaxis when acute GVHD developed) should be continued at therapeutic doses adjusted as necessary for renal, central nervous system (CNS) or other toxicity using conventional management guidelines.

#### 2.5.6. Topical and Ancillary GVHD Therapies

Topical skin therapy for acute GVHD, including skin creams, as well as GI topical agents (e.g., beclomethasone or budesonide), are not encouraged on trial, however are not prohibited. Use of topical agents for management of acute GVHD will be recorded as a secondary endpoint assessment in this trial. No rules or guideline for taper and discontinuation for topical agents is provided in this protocol.

Ancillary/supportive care measures for acute GVHD such as the use of anti-motility agents for diarrhea, including octreotide, is allowed at the discretion of the treating physician. Use of ursodiol to prevent/reduce gall bladder sludging, or prevent hepatic transplant complications is also allowed according to institutional guidelines.

#### 2.5.7. Management of study therapy after GVHD Progression or Non-response:

The following guidelines describe intended management of initial randomized therapy and thresholds for starting secondary therapy:

1. Initial randomized therapy should be given for at least 4 days before considering initiation of secondary therapy. As progressive manifestations of GVHD (new organ involvement or increased organ specific symptoms sufficient to increase the organ stage by one or more) can be ultimately stabilized and controlled in this initial therapy timeframe, secondary therapy should only be considered if GVHD continues to progress after this period.

2. If no response (no improvement in any affected organ) is observed after 7-10 days of initial randomized therapy, secondary therapy can be considered.

# CHAPTER 3

# **3. STUDY ENDPOINTS**

# **3.1. Primary Endpoint**

The primary endpoint is the rate of complete remission (CR)/partial remissions (PR) on Day 28 post-randomization in patients with standard-risk acute GVHD (defined by both refined Minnesota clinical standard-risk criteria and AA1/2 biomarker risk group). Scoring of CR/PR are in comparison to the participant's acute GVHD status (score) on the day of randomization.

# **3.1.1.** Response Definitions

Scoring of CR, PR, MR, NR and progression are in comparison to the participant's acute GVHD status (score) on the day of randomization.

**CR is defined as a score of 0 for the GVHD grading in all evaluable organs.** For example, for a response to be scored as CR at Day 56 or later, the participant must still be in CR on that day and have had no intervening additional therapy for an earlier progression, PR or NR.

**Partial response (PR) is defined as improvement in one or more organs involved with GVHD symptoms without progression in others.** For example, for a response to be scored as PR at Day 28 or later, the participant must still be in PR on that day and have had no intervening additional therapy for an earlier progression, PR or no response (NR).

Mixed response (MR) is defined as improvement in one or more organs with deterioration in another organ manifesting symptoms of GVHD or development of symptoms of GVHD in a new organ.

Progression is defined as deterioration in at least one organ without any improvement in others.

No response (NR) is defined as absence of any improvement or progression as defined. Patients receiving secondary therapy (including need to re-escalate steroid dose to  $\geq 2.5$  mg/kg/day of prednisone [or methylprednisolone equivalent of 2 mg/kg/day]) will be classified as non-responders. Patients who are assigned to the sirolimus arm who require initiation of systemic corticosteroids for the treatment of acute GVHD will be considered as non-responders for purposes of primary endpoint assessment.

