#### Post-Randomization

The following post-randomization assessments are required of all patients, regardless of therapy received.

- 1. Karnofsky or Lansky performance status at Days 56, 90, 180 and 365
- 2. Complete acute GVHD staging and grading information including assessments of rash, diarrhea, nausea/vomiting, weight and liver function tests weekly through Day 56; Day 90, 6 and 12 months
- 3. Chronic GVHD evaluation (if present) Day 28, 56, 90, and 6 and 12 months
- 4. CBC with differential, chemistry (including liver function tests) weekly through Day 56; Day 90, 6, and 12 months
- 5. Fasting lipid profile at Day 28, 56, and 6 months
- 6. Toxicity evaluation weekly through Day 56; Day 90, 6 months and 12 months
- 7. Recording of all systemic immune suppression, including steroid dose and drug levels (as appropriate for sirolimus, cyclosporine, tacrolimus) weekly through Day 56, Day 90, 6, and 12 months. Second-line immune suppressive therapy (therapy beyond initial

randomized therapy of either sirolimus or prednisone) should be recorded at each of these time points.

- 8. Use of topical (skin, GI) steroid agents weekly through Day 56; Day 90, 6 and 12 months.
- 9. Data on systemic infections, and EBV PTLD (or EBV requiring therapy), recorded as per the BMT CTN (Technical) MOP through 12 months.
- 10. EBV & CMV monitoring as per institutional practice.
- 11. Myopathy assessments at Day 56 and 6 months.\*
  - a. Hip Flexor and Quadriceps Strength via handheld dynamometer
  - b. Two Minute Walk Test
  - c. 5-time Sit-to-Stand
  - d. Adult Myopathy Assessment Tool (AMAT)
- 12. Patient reported outcomes (M.D. Anderson Symptom Inventory, FACT-BMT, SF-36, or PedsQL (Pediatrics)) at Day 56, 6 months and 1 year.\* Only English speaking adult and pediatric patients, and Spanish speaking adult patients are eligible to participate in the Health Quality of Life (HQL) component of this trial. Patients >18 years will complete the FACT-BMT, MOS SF-36 and MDASI instruments. Patients ≥ 8 years through 18 years will complete the PedsQLTM Stem Cell Transplant Module.
- 13. OPTIONAL 30-40 mL blood samples for research laboratory studies at Day 7, 28, and 56 (see Appendix B).\* Patients with weight <13 kg will have ≤3 mL/kg collected at each individual time point.

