### **1.2.2 Accrual Plan and Randomization**

The target sample size of the study is 120 participants with AA1/2 biomarker status. It is expected that 80% of all randomized participants will have AA1/2 status. This requires 150 total participants to be randomized in order to obtain the targeted number of AA1/2 participants.

The estimated accrual period is 2 years.

Participants will be randomized to sirolimus or prednisone treatment in a 1:1 ratio. Randomization is stratified by treatment center using permuted blocks of randomly chosen sizes of 2 or 4.

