## 2.8 Analysis Populations

### 2.8.1 Primary Analysis Population

Participants will be analyzed according to the intent to treat (ITT) principle for this study, i.e. according to the treatment groups to which they were randomized, regardless of whether the assigned treatment was administered. Any participant who receives a treatment randomization number will be considered to have been randomized. Since the primary interest of this study is treatment in participants with standard risk acute GVHD, the primary analysis population will consist of all randomized AA1/2 participants with treatment classified per the ITT principle.

The primary analysis for the primary, secondary, and exploratory endpoints will use the primary analysis population. A secondary analysis of the primary endpoint will be

performed, classifying participants by the initial treatment actually given. Another secondary analysis will consider primary and key secondary outcomes for all randomized AA3 participants classified per the ITT principle. An analysis of safety endpoints will also be conducted using the safety analysis population as described below. Analyses of each endpoint and population used will follow the analysis plan as described below in section 4 of this SAP.

If a participant is deemed not eligible for the study after study registration or randomization occurs, he will be excluded from all analysis populations.

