## 4. Analysis Plan

### 4.1 Analysis of the Primary Endpoint

The primary endpoint for this study is complete response/partial response (CR/PR) of acute GVHD to therapy at Day 28 post-randomization. No formal hypothesis test will be performed. Instead, the difference in response rates between the two arms will be estimated with a 90% confidence interval.

Acute GVHD response is categorized as complete response (CR), partial response (PR), mixed response (MR), no response (NR), and progression and is scored relative to the participant's acute GVHD status (organ staging) entered on the day of randomization. Response categories are defined as follows:

- **Complete response (CR):** A stage of 0 for the GVHD grading in all evaluable organs. For example, for a response to be scored as CR at Day 28, the participant must still be in CR on that day and have had no intervening additional therapy for an earlier progression, PR or NR.
- **Partial response (PR):** Improvement in one or more organs involved with GVHD symptoms without progression in others.
- **Mixed response (MR):** Improvement in one or more organs with either deterioration in another organ manifesting symptoms of GVHD or development of symptoms of GVHD in a new organ.
- **Progression:** Deterioration in at least one organ without any improvement in others.
- **No response (NR):** Absence of any improvement or progression

Patients receiving secondary therapy (including need to re-escalate steroid dose to  $\geq 2.5$  mg/kg/day of prednisone [or methylprednisolone equivalent of 2 mg/kg/day]) will be classified as non-responders. Patients who are assigned to the sirolimus arm who require initiation of systemic corticosteroids for the treatment of acute GVHD will be considered as non-responders for purposes of the primary endpoint assessment.

Participants that have died prior to Day 28 will be treated as nonresponders in the analysis.

The reference for response evaluation is the GVHD organ staging reported at enrollment. The response rate (CR/PR) at Day 28 will be estimated using frequencies in each treatment group. A 90% Wald confidence interval for the difference in rates of the treatment groups will be computed.

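### The secondary analysis by initial treatment given keeps a corticosteroid-start failure rule tied to the assigned arm; read literally, it can fix non-response for some prednisone-treated participants

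*Protocol*

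**What the plan says.** The primary analysis population in SAP 2.8.1 is all randomized AA1/2 participants, grouped as assigned "regardless of whether the assigned treatment was administered". The same section adds a secondary analysis of the primary endpoint, "classifying participants by the initial treatment actually given". I take this to be among AA1/2 participants, since AA3 participants have their own analysis. The section then states: "Analyses of each endpoint and population used will follow the analysis plan as described below in section 4 of this SAP".

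The only scoring of Day 28 response in SAP section 4 is in 4.1. It contains two failure rules beyond organ staging and death:

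- A general rule with no arm restriction: anyone who receives secondary therapy, including steroid re-escalation to the stated threshold, is a non-responder.
- An arm-specific rule: "Patients who are assigned to the sirolimus arm who require initiation of systemic corticosteroids for the treatment of acute GVHD will be considered as non-responders".

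Protocol 3.1.1 carries the same two rules, the second again worded by assignment: "Patients who are assigned to the sirolimus arm who require initiation of systemic corticosteroids". SAP 4.1 does not mention the analysis by treatment given, and Exhibit 1501-3 has no shell for it.

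**The concern.** In this analysis the group is defined by the drug received and part of the outcome by the arm assigned. A participant assigned to sirolimus whose first treatment was prednisone has been started on systemic corticosteroids for acute GVHD. Under the literal rule that participant is a non-responder even with stage 0 in every organ at Day 28, and is counted in the prednisone group. A prednisone-assigned participant on the same drug is scored on staging. Two people in the same column are then scored by different rules, and the difference lowers the prednisone rate.

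The hypothesis is comparable response, the trial is open label, and the result is an estimate rather than a test. A supportive estimate that moves toward sirolimus through scoring alone could be read as added reassurance. It differs from the ITT estimate only through the regrouped participants, so how they are scored decides what the analysis adds.

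**Working it through.** **Inputs.** 60 AA1/2 participants per arm, from 120 analyzed at 1:1 (SAP 1.2.2, Table 2.1). Response of 60% on both drugs, or 50% on sirolimus and 60% on prednisone (the two scenarios in SAP 2.1). A 90% Wald interval (SAP 4.1). The number k of sirolimus-assigned participants who start on prednisone is not in the documents; I **assume** k = 0 to 6.

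**Reproducing the plan's figure.** The half-width is 1.645 × √(p₁(1−p₁)/n₁ + p₂(1−p₂)/n₂). At 60% in both arms and 60 per arm this is 1.645 × √(0.24/60 + 0.24/60) = 14.7 points. The lower bound is −14.7%, against −15% in the plan. At 50% versus 60% the lower bound is −24.9%, against −25%.

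**Effect of the literal rule, 60% on both drugs.** After regrouping, the sirolimus group has 60 − k participants and a rate of 0.6(60 − k)/(60 − k) = 60%. The prednisone group has 60 + k.

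- Literal rule: the k regrouped participants all fail, so the prednisone rate is 36/(60 + k).
- Rule tied to the drug given: (36 + 0.6k)/(60 + k) = 60%, so the difference is 0 for every k.
- ITT: the k participants fail in the sirolimus arm, so the difference is 0.6(60 − k)/60 − 0.6.

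| k | Prednisone rate, literal rule | Difference (sirolimus minus prednisone), literal rule, 90% CI | Difference, rule by drug given | ITT difference |
|---|---|---|---|---|
| 0 | 60.0% | 0.0 (−14.7 to 14.7) | 0.0 | 0.0 |
| 1 | 59.0% | +1.0 (−13.8 to 15.7) | 0.0 | −1.0 |
| 2 | 58.1% | +1.9 (−12.8 to 16.7) | 0.0 | −2.0 |
| 3 | 57.1% | +2.9 (−11.9 to 17.7) | 0.0 | −3.0 |
| 6 | 54.5% | +5.5 (−9.4 to 20.4) | 0.0 | −6.0 |

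At k = 3 the estimate moves 5.9 points from ITT to the analysis by treatment given (−3.0 to +2.9). Of this, 2.9 points are scoring artefact.

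**50% versus 60%, k = 6.** The sirolimus group stays at 50%. The prednisone group is 36/66 = 54.5%. The literal difference is −4.5 points; with the rule tied to the drug given it is −10.0.

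**Reverse crossover.** Consider a participant assigned to prednisone, first given sirolimus and later given prednisone. The arm-specific rule does not reach this participant. The general secondary-therapy rule may, because prednisone added after sirolimus is additional therapy on a natural reading. The Post-Randomization list in Protocol 4.4 describes second-line therapy as therapy beyond the initial "randomized therapy of either sirolimus or prednisone) should be recorded at each of these time points". For this participant prednisone is the randomized drug, so that wording points the other way, but it is a recording instruction and not a scoring rule. The texts do not settle the case, so I attach no size to it.

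**The case against.** The strongest reply is that the rule speaks of participants who require corticosteroids to be started. It follows the secondary-therapy rule, and Protocol 2.5.7 presents secondary therapy as a response to progression or non-response. Someone given prednisone first did not clearly require it in that sense. This is a reasonable reading, but neither document states it, and two programmers could derive the flag differently. Endpoint Review Committee adjudication does not close the gap either: SAP 2.2 describes it for missing primary-endpoint data, and SAP 2.6 leaves its scope to a charter.

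A second reply is that few participants, or none, will be regrouped. This largely stands. Enrollment carries a commitment to the assigned drug, and the first dose is due within 24 hours of randomization. Those free to change therapy at the physician's discretion (AA3 or missing result) are outside this population, and later switching does not regroup anyone because grouping is by initial treatment. One regrouped participant moves the estimate 1.0 point against a half-width of about 14.7.

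A reader might go further and infer that both crossover directions favour sirolimus. The documents do not support that, because the general secondary-therapy rule has no arm restriction and may already make the reverse case a failure. A reader might also take this analysis to be a formal safeguard against dilution of the ITT estimate. SAP 2.8.1 states no such purpose and attaches no decision to it.

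**Conclusion.** The concern holds for one direction of crossover in one supportive analysis. As written, participants assigned to sirolimus and first treated with prednisone can be fixed as non-responders in the prednisone group, which shifts the sirolimus-minus-prednisone difference upward. With 60 per arm and 60% response on both drugs, the shift is about 1 point per participant: 0 if nobody crosses over and +5.5 points at 6 of 60. That range is an assumption, and 6 is its extreme. The size also rests on the literal reading of the rule.

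It would be wrong to conclude that the primary result is biased by this mismatch. In the ITT analysis both grouping and rule follow assignment, and in the equal-response example any crossover of this kind moves the ITT difference against sirolimus. No margin, test or decision depends on the supportive analysis. What remains is a stated rule that gives a biased answer where it is applied, and it is cheap to correct.

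**What to change.** Amend SAP 2.8.1 and 4.1 before data lock, so that the choice is not made with the results in view. For the analysis by initial treatment actually given only, state that:

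- the corticosteroid-start rule applies to participants whose initial treatment was sirolimus;
- the general secondary-therapy rule, including re-escalation, continues to apply to all participants, with secondary therapy judged relative to the initial treatment actually given.

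The second statement keeps the general rule from being narrowed to one drug and also settles the reverse crossover. Report the number regrouped in each direction next to the estimate. Leave the ITT scoring unchanged. The cost is a short SAP addition and one changed derivation flag; no new data are needed.
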